## **STUDY OBJECTIVES**

1. The primary objective of this study is to compare ultrasound-guided block of the transversus abdominis plane (TAP) vs. laparoscopic-guided TAP block, versus no TAP block on opioid consumption in the first 24 hours following colorectal surgery.
2. The secondary objective of this study is to assess the impact of these adjunctive regional techniques on overall patient satisfaction, postoperative pain scores, length of postoperative hospital stay, postoperative ileus, and adverse events directly related or unrelated to TAP block in the 30-day postoperative period.

## **BACKGROUND AND SIGNIFICANCE**

Postoperative pain can pose significant challenges in the postoperative recovery of patients undergoing major colorectal surgery. Traditionally, opioids have played an important role in treating postoperative pain. It is well established that opioids are highly effective in relieving pain; however opioids are associated with numerous side effects that include nausea, vomiting, constipation, ileus, bladder dysfunction, respiratory depression, pruritus, drowsiness, sedation, and allergic reaction. These opioid side effects, which range in severity, can significantly interfere with discharge home following colorectal surgery. (1) Significant interest exists in the use of local anesthetic based regional anesthesia techniques as a means to extend the analgesic window for patients undergoing colorectal surgery (2). Specifically, the use of the TAP block as an adjunct in postoperative pain control has been widely reported in the anesthesia and colorectal surgery literature (2,3). Historically, the block was performed in a blind fashion with relative success and presently the block is typically performed either with ultrasound guidance or laparoscopic visualization (2,3). While TAP block has shown to be effective in post-operative pain control, the techniques used to place the block have not formally been compared.

We are purposing a prospective, patient-blinded, randomized study of patients undergoing major colorectal surgery to compare TAP block under ultrasound guidance versus laparoscopic visualization versus no TAP block. We hypothesize that laparoscopic-guided TAP block is non-inferior to ultrasound-guided TAP block with respect to perioperative pain control and either technique is superior to no TAP. In addition we will measure procedural time, any adverse events related to the block, overall postoperative analgesic requirement, analgesic duration, postoperative pain scores, length of postoperative hospital stay, incidence of postoperative ileus, and overall patient satisfaction between the three groups.

## **STUDY DESIGN**

The proposed study is a patient-blinded, prospective randomized study to compare ultrasound-guided block of the TAP versus laparoscopic-guided TAP block versus no TAP block in patients undergoing major colorectal surgery. The primary outcome measure is analgesic requirement in morphine equivalents in the first 24 hours after surgery. Secondary outcome measures include overall postoperative analgesic requirement, postoperative pain scores, length of postoperative hospital stay, any adverse events related to TAP block, overall perioperative complications in the 30-day postoperative period and overall patient satisfaction after major colorectal surgery.

All groups will receive general anesthesia as the primary mode of anesthesia. Patients randomized to one of two treatment arms will also undergo either ultrasound-guided or laparoscopic-guided TAP block in the operating room at the conclusion of the procedure. Patients randomized to no TAP will not have a TAP block performed but will receive all routine intraoperative and postoperative analgesia as deemed appropriate by the anesthesia and primary surgical team. A standardized preoperative non-opioid pain regimen will be utilized. In the recovery room, short acting opioids for breakthrough pain will be available. Opioids will also be administered for rescue if need be. All patients will receive postoperative intravenous narcotics via patient controlled analgesia (PCA) device.

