### **II. In the preoperative holding area:**

- a) An anesthesia investigator assigned to the specific case will assess patients and perform a pre-operative anesthesia assessment as per standard protocol at CSMC. None of this data will be recorded until written informed consent is obtained.
- b) Patients will provide a detailed medical history including demographic information (e.g., age, weight, height, ethnic origin, smoking history, history of motion sickness, history of postoperative nausea and vomiting, as well as chronic analgesic usage). None of this data will be recorded until written informed consent is obtained.
- c) Written informed consent will be obtained by one of the investigators.
- d) Patients will be randomized in a blinded fashion by study staff to one of the groups via online randomization site, sealedenvelope.com, in a 2:2:1 fashion.

Group 1	n=100	Ultrasound guided TAP Block
Group 2	n=100	Laparoscopic guided TAP Block
Group 3	n=40	No TAP

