### III. During the intraoperative period

- a) Standard anesthesia monitors will be applied: automatic blood pressure cuff, three-lead electrocardiography, capnography, and pulse oximetry will be used continuously.
- b) Induction of general anesthesia will be with propofol 2-3 mg/kg & a non-depolarizing muscle relaxant (choice will be operator dependent). Maintenance of anesthesia will be with an inhalational anesthetic.
- c) The study staff performing randomization will instruct the anesthesiologist or surgeon to either block the transversus abdominis plane with ultrasound, laparoscopy, or no block.
- d) For the block, a standard weight based dose (bupivacaine 0.25% with epinephrine 1:200,000, at a 1ml/kg dose) will be used for both ultrasound-guided or laparoscopic-guided block.
- e) The block is administered between the costal margin and iliac crest in the anterior axillary line at 2 different sites on each side (4 injections total).
- f) For ultrasound-guided TAP block, after the surgeons have completed their portion of the procedure, a member of the anesthesia research team will use sterile technique to prep the abdomen. The block is then placed bilaterally (at 2 different sites on each side of the abdomen) in the anterior axillary line, between the costal margin and iliac crest in the intermuscular plane between the internal oblique and transversus abdominis muscles using ultrasound guidance.
- g) For laparoscopic-guided TAP block, the attending surgeon will perform the block at the conclusion of the procedure under laparoscopic guidance. Bilateral TAP block will be performed in the anterior axillary line between the costal margin and iliac crest. After the needle is passed through the skin, it is continued until 2 distinct “pops” are felt, indicating the needle pierced each of the 2 fascia layers (external oblique and internal oblique fascia).

After injection of the correct plane, a smooth raised area of fluid covered by transversus abdominis muscle is seen with the laparoscope. The laparoscopic vision also assures that the preperitoneal plane is not injected and that the injection does not go intraperitoneal.

- h) Dose of anesthetics, analgesics, local anesthetics, and IV fluid therapy during the operation will be recorded in the anesthesia record as per standard procedure. A copy of the sonographic image will be collected for each patient at the conclusion of the block.

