#### IV. PACU

- a) Verbal rating scale (VRS) for pain will be assessed by the PACU RN upon arrival to recovery room, then every 30min interval until discharge.
  - o Requirements for “rescue” analgesic medication will be recorded before discharge.
- b) Any adverse events during the perioperative period will also be noted by PACU RN.

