#### V. Following completion of surgery (post-operative):

- a) Anesthesia will be discontinued at skin closure.
- b) Patients will be transferred to the recovery room after emergence from sedation
- c) Treatment of surgical pain prior to discharge from the recovery room: moderate-to-severe pain (VRS > 7): hydromorphone, 1-1.5 mg IV, moderate pain (VRS of 4-6): hydromorphone 0.5 - 1 mg IV., mild pain (VRS 2-3), hydromorphone 0.1-0.2 mg IV. Patient pain control medication will continue with the initial treatment medication for all subsequent rescue doses as needed until recovery room discharge.
- d) Patient nausea, vomiting, or retching will be initially treated with ondansetron 4mg IV. Patients unresponsive to ondansetron will receive metoclopramide 10mg IV.
- e) Patient discharge criteria from PACU will include: awake and alert, and has stable vital signs.

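### Only the patient is stated to be blinded: nothing keeps the arm from the nurses who score pain, and nothing masks the injection sites that separate TAP from no TAP

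*Combined protocol and SAP*

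**What the plan says.** **Who is blinded.** BACKGROUND AND SIGNIFICANCE and STUDY DESIGN both describe blinding of the patient only: "The proposed study is a patient-blinded, prospective randomized study". The section on the preoperative holding area says "Patients will be randomized in a blinded fashion by study staff to one of the groups via online randomization site", which describes how allocation is made, not who is masked afterwards.

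**Who is told the arm.** Under the intraoperative period: "The study staff performing randomization will instruct the anesthesiologist or surgeon to either block the transversus abdominis plane with ultrasound, laparoscopy, or no block". The same section says "Dose of anesthetics, analgesics, local anesthetics, and IV fluid therapy during the operation will be recorded in the anesthesia record as per standard procedure". It describes no masking of that entry and does not say who reads it.

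**Who scores pain and how rescue is given.** Under PACU, the verbal rating scale (VRS) "will be assessed by the PACU RN upon arrival to recovery room" and is repeated every 30 minutes. The postoperative section ties hydromorphone to the VRS in three tiers, each a range (the top one is "hydromorphone, 1-1.5 mg IV"). It names no one as choosing within a range. Nursing staff record later scores, to 72 hours.

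**What differs on the skin.** Both TAP arms have two injections on each side, four in all, in the same area. In contrast, "Patients randomized to no TAP will not have a TAP block performed". No sham, dressing or other cover is described.

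**What is analysed.** The primary outcome is opioid use in morphine equivalents over the first 24 hours after surgery. Nothing excludes PACU rescue from it, and doses of all opioids are to be recorded. All patients also have PCA.

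**The concern.** Part of the 24-hour opioid total is created by staff. A nurse elicits the VRS, the VRS selects a tier, and someone chooses a dose within it. STUDY DESIGN also leaves the no-TAP arm's analgesia to the judgement of the anesthesia and surgical teams, which include people told the arm. If those involved know or guess who had a block, expecting more pain without one could raise scores or doses in the no-TAP arm and enlarge the apparent benefit of TAP.

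The patient's own blinding has no stated mechanism for block versus no block. Four puncture marks against none can inform the patient, who operates the PCA.

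For ultrasound versus laparoscopic the exposure is narrower. Someone would have to learn the technique from the record or the operating team and also favour one technique.

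**Working it through.** **Step 1. Which route reaches which comparison**

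| Route | TAP v no TAP | Ultrasound v laparoscopic |
|---|---|---|
| Visible injection sites (four v none; same plan in both TAP arms) | Yes | No |
| Local anesthetic dose in the anesthesia record | Possible; readers not stated | Only if the entry shows the technique |
| Operating team telling others | Possible; not prohibited | Possible; not prohibited |
| Residual sensory blockade check during admission | Yes, may show a block | Not by itself |

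The first comparison is the one powered under Secondary outcome measure, although the stated primary objective covers all three arms. The second is powered under Primary outcome measure.

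**Step 2. Reproduce the plan's figures**

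Inputs from Data Analysis: SD 25 mg; limit 10 mg, one-sided 0.025, 100 per TAP arm; superiority difference 15 mg (60 v 45), two-sided 0.05, 40 v 100.

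- Standard error = SD × √(1/n₁ + 1/n₂).
- Ultrasound v laparoscopic: 25 × √(2/100) = 3.54 mg. Noncentrality 10/3.54 = 2.83, 198 df: power 80.4% (plan: 80%).
- TAP v no TAP: 25 × √(1/40 + 1/100) = 4.68 mg. Noncentrality 15/4.68 = 3.21, 138 df: power 89.0% (plan: 88%).

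Both agree with the plan, so the same model serves for the next step.

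**Step 3. Add an assumed bias**

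The documents give no bias estimate, no number of rescue doses and no opioid conversion. The shifts of 1 and 2 mg morphine equivalents in the arm mean are therefore assumptions. With bias b:

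- Superiority error: no true difference, noncentrality b/4.68, both tails.
- Non-inferiority error: true difference at the 10 mg limit, bias favouring the laparoscopic arm, noncentrality b/3.54.
- Non-inferiority power: true difference 0, bias against the laparoscopic arm, noncentrality (10 − b)/3.54.

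| Assumed shift | Superiority error, two-sided | Non-inferiority error | Non-inferiority power, opposite shift |
|---|---|---|---|
| 0 mg | 5.0% | 2.5% | 80.4% |
| 1 mg | 5.5% | 4.7% | 71.7% |
| 2 mg | 7.1% | 8.1% | 61.5% |

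No sample-size figure in the plan changes.

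**The case against.** Patient-only blinding is a declared choice, and the operators cannot be blinded. Every patient has a PCA, and the VRS is the patient's own verbal rating, so much of the outcome lies outside staff control. Both safeguards stand, but they have limits: PACU rescue is also available, and PCA use is protected from expectation only while the patient cannot tell the arm.

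A reader might infer three stronger things that the documents do not support:

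- **That nurses see the allocation and pick the dose.** No section says so. The PACU section gives the nurse the VRS and the noting of adverse events; the dose section names no one. What can be said is that nurses are not stated to be blinded.
- **That puncture marks undermine the ultrasound versus laparoscopic comparison.** Both arms have the same injection area and number, so the marks do not separate them. No section shows a staff preference for either technique.
- **That the bias is 2 to 3.5 mg.** This takes the full 0.5 mg width of either of the top two tiers and assumes 4 to 7 mg morphine per mg hydromorphone. Applied to arm means, with one dose each, it requires one arm always at the top of the range and the other always at the bottom. The errors would then be 8.1-16.5% (non-inferiority) and 7.1-11.5% (superiority). The arithmetic is right but the scenario is extreme for a single dose. With the number of doses unknown, the true figure could be smaller or larger.

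**Conclusion.** The concern holds in limited form. The plan does not say who is blinded after surgery and gives no means of hiding block from no block, while part of the 24-hour opioid outcome passes through staff. The site risk belongs to TAP versus no TAP. For ultrasound versus laparoscopic the only routes are the record and the operating team.

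The error rates in the table are illustrations. They rest on an assumed 1 to 2 mg shift in means, the plan's SD of 25 mg and full planned numbers, and the non-inferiority figure also needs the bias to favour the laparoscopic arm. They show that a shift that is small beside the 10 mg limit is not negligible; they do not show that such a shift will occur. This is a cheap improvement, best made before enrolment because analysis cannot restore lost blinding.

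**What to change.** 1. In STUDY DESIGN, the intraoperative section and the PACU section, state that PACU and ward nurses who score pain or give opioid are not told the arm, and that the operating team does not disclose it at handover.
2. Place identical small dressings over the four TAP sites in all three arms before the patient leaves the operating room. No sham injection is needed.
3. Reconcile the dressings with the injection-site monitoring described under POTENTIAL RISKS, and the masking with the residual sensory blockade check during admission, for example by recording that check after the pain score.
4. Leave the actual drug entry in the record and available for safety, since the protocol names local anesthetic toxicity as a risk.

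The cost is a protocol amendment, four dressings per patient and a handover instruction. Masking will remain incomplete, because the record and the sensory check can still reveal a block. No dose, analgesia order or sample size needs to change.

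### PCA opioid counts in the 24-hour primary outcome, but nothing requires the pump to be ordered the same way in all arms or by someone unaware of the arm

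*Combined protocol and SAP*

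**What the plan says.** The outcome is defined in STUDY DESIGN: "The primary outcome measure is analgesic requirement in morphine equivalents in the first 24 hours after surgery". The same section says "All patients will receive postoperative intravenous narcotics via patient controlled analgesia (PCA) device". That sentence is all the protocol says about PCA. No section gives a drug, bolus, lockout, limit, background infusion, start or stop time, or says who writes the order.

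The rest of the analgesic plan does not fill the gap:

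- **Before surgery.** "A standardized preoperative non-opioid pain regimen will be utilized". This is the only regimen described as standardized.
- **Recovery room and rescue.** "In the recovery room, short acting opioids for breakthrough pain will be available. Opioids will also be administered for rescue if need be". The hydromorphone bands in section V of STUDY METHODS are introduced by "Treatment of surgical pain prior to discharge from the recovery room", so they end when the patient leaves recovery.
- **No TAP arm.** These patients "will receive all routine intraoperative and postoperative analgesia as deemed appropriate by the anesthesia and primary surgical team". There is no matching sentence for the two TAP arms.

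On blinding, STUDY DESIGN states "The proposed study is a patient-blinded, prospective randomized study". No one else is described as blinded. Section III, item c says "The study staff performing randomization will instruct the anesthesiologist or surgeon" which block to give, if any. Section VI records opioid doses but does not mention PCA settings.

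**The concern.** With PCA, the 24-hour total depends on two things: how often the patient presses, and what the clinician has set (milligrams per press, limits, any background infusion). Blinding the patient protects the first only. If whoever sets the pump knows the arm and programs it differently as a result, the recorded milligrams differ without any difference in pain, and all of that difference enters the primary outcome.

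Both main conclusions are exposed. The comparison of ultrasound with laparoscopic TAP uses a 10 mg limit, and the comparison of TAP with No TAP is planned on a 15 mg difference. Spread over 24 hours these are 10/24 = 0.42 mg/h and 15/24 = 0.63 mg/h, so a modest programming difference is not negligible beside them. The bias can run in either direction. Because settings are not listed among the recorded data, the planned data would not show whether it had happened.

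**Working it through.** **Inputs from Data Analysis.** SD 25 mg. Ultrasound vs laparoscopic: 100 per arm, one-sided 0.025, limit 10 mg, expected difference 0, stated power 80%. TAP vs No TAP: 100 and 40, two-sided 0.05, difference 60 − 45 = 15 mg, stated power 88%.

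**Method.** Standard error SE = 25 × √(1/n₁ + 1/n₂). Rejection probability = P(T > t₀.₉₇₅), where T is noncentral t with n₁ + n₂ − 2 degrees of freedom and noncentrality λ = (distance from the null)/SE.

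**The plan's own figures.**
- Ultrasound vs laparoscopic: SE = 25 × √(2/100) = 3.54 mg; λ = 10/3.54 = 2.83; power 80.4%. The plan states 80%.
- TAP vs No TAP: SE = 25 × √(1/40 + 1/100) = 4.68 mg; λ = 15/4.68 = 3.21; power 89.0%. The plan states 88%.

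Both reproduce closely. The sample-size figures are not in question.

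**Assumed shift.** The documents give no size for a programming effect. For illustration only, and not as a suggested regimen, let b be the net mean shift from a background infusion used more often in one arm, with no offset from fewer presses:
- Smaller case: 0.5 mg/h × 24 h × 10 percentage points = 1.2 mg.
- Half of the larger case: 2.4 mg.
- Larger case: 1 mg/h × 24 h × 20 percentage points = 4.8 mg.

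**Effect on the conclusions.**

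| Net shift b | False non-inferiority: true difference 10 mg, shift favors laparoscopic, λ = b/3.54 | Non-inferiority power: true difference 0, shift against laparoscopic, λ = (10 − b)/3.54 | TAP falsely found better: true difference 0, extra opioid in No TAP, λ = b/4.68 |
|---|---|---|---|
| 0 | 2.5% | 80% | 2.5% |
| 1.2 mg | 5.2% | 70% | 4.4% |
| 2.4 mg | 9.9% | 57% | 7.3% |
| 4.8 mg | 27% | 31% | 17% |

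The second and third columns need shifts in opposite directions, so they are alternatives.

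**Direction for TAP vs No TAP.** The last column is one tail of the two-sided test and requires the extra opioid to be in No TAP. If the 4.8 mg were in a TAP arm, the total rejection rate would be 17.5%, but 17.3 points of that would show TAP worse and only 0.14 points TAP better. The risk of a false superiority claim therefore arises only from extra opioid in No TAP.

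**The case against.** The strongest reply is that the protocol is silent, not that it prescribes unequal care. PCA is given to all patients, and nothing says settings differ by arm. The sentence allowing discretion covers No TAP only. Item c of section III says who is told to give the block, not who writes PCA orders. The two TAP arms receive the same weight-based local anesthetic at the same sites, so the documents give no reason to program them differently, and variation unrelated to arm adds variance rather than bias. A blinded patient can also press less when more is delivered. Finally, one fixed set of starting settings would sit badly with ages 18 to 90, ASA I to III, and chronic analgesic users, whose use is recorded and who are not excluded.

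Most of this stands, and it limits the point. A reader might infer that PCA is the main source of the outcome, that it runs through the whole 24 hours, or that its settings are left in every arm to teams who know the allocation. The documents support none of these. Recovery-room and rescue opioids also count and no split is given; no PCA start or stop time is stated; and the person who programs the pump is not identified.

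The reply does not remove the gap. In an opioid-dose trial where only the patient is said to be blinded, no passage prevents arm-related programming or would reveal it. The spread of patients argues for an order that can vary with the patient, not with the arm.

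**Conclusion.** The concern holds in a limited form. PCA opioid enters the primary outcome in all three arms; the protocol does not require the drug and settings to be chosen in the same way in each; and it does not say who programs the pump or whether that person is blinded. The exposure is most direct for TAP vs No TAP, because the discretion is written for No TAP. For ultrasound vs laparoscopic it rests on silence alone.

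The size is conditional. The percentages in the table rest on an assumed net shift of 1.2 to 4.8 mg, the plan's SD of 25 mg, and no compensating fall in presses, which would shrink them. The documents do not show that any such shift would occur. The change is still worth making before the trial runs, because it alters conduct, costs little, and closes a route to bias that could not be examined afterwards from the data the plan lists.

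**What to change.** In STUDY DESIGN, state that PCA orders in all three arms come from one common order set, chosen before the allocation is revealed or by someone unaware of it, and changed only under one written rule common to all arms. The order may vary with patient characteristics but not with arm. Its content is for the sponsor and site to decide. Reconcile the No TAP discretion sentence with this wording.

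In section VI of STUDY METHODS, add PCA settings and any changes to the opioid doses already recorded, and report them by arm. A split of patient-demanded from clinician-set opioid can be shown, but only as description: settings also affect how often patients press, so the split does not give an unbiased comparison.

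The cost is protocol wording, a shared order set, a few extra data fields, and some loss of clinician freedom in the initial order. No extra patients are needed.
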